3.6. SAMPLE SIZE

Considering the primary endpoint of the study as the reduction from baseline to week 8 in LDL cholesterol level and the data available from literature [Phytomedicine. 2016 Oct 15; 23(11):1113-8], a reduction of LDL level of approximately 10% is expected after the intake of the nutraceutical. Therefore, a mean difference of 15 mg/dL in the reduction of LDL cholesterol level at week 8 between the nutraceutical treatment group and the placebo group is considered clinically significant.

Assuming a baseline LDL level of 145 ± 19 mg/dL, a power of 90% and a 5% two-sided alpha level to detect a difference in mean change in LDL from baseline to week 8 equal to 15 mg/dL between the nutraceutical and the placebo group, the total number of patients to be evaluated should be 35 per treatment arm in a 1:1 ratio (NQuery Advisor, 7.0). Allowing for an approximate 20% dropout rate, at least 88 patients should be randomized: 44 patients in each treatment group.

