6.5. EFFICACY EVALUATION

6.5.1. Primary efficacy analysis

The statistical analysis of the primary variable will be performed on the FAS population. Summary statistics of LDL cholesterol levels and change from baseline at each assessment time point will be presented overall and by planned treatment group by means of descriptive statistics for continuous data.

An analysis of covariance (ANCOVA) model will be estimated on the changes from baseline to Week 8 in LDL cholesterol levels considering planned treatment group as factor and baseline value of LDL cholesterol as continuous covariate. Results will be reported as Least-Square Means together with associated two-tailed 95% CI; the difference between Least Square Mean of nutraceutical combination group versus placebo will be estimated with two-tailed 95% CI and p-value.

If the assumption of normality of residuals is violated, the ANCOVA model will be fitted on rank transformed data.

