6.5.3. Secondary efficacy analysis

The statistical analyses of the secondary variables will be performed on the FAS population. Summary statistics for each secondary variable (i.e. total blood cholesterol, blood HDL-cholesterol, blood non-HDL cholesterol, blood triglycerides, apolipoprotein B, TC/HDL and LDL-c/HDL risk ratios, pulse volume(PV) waveform, glycemia, ALT AST, gamma-GT, creatinine, uric acid, CPK) and change from baseline at each assessment time point will be presents overall and overall and by planned treatment group by means of descriptive statistics for continuous data.

For each secondary variable, an analysis of covariance (ANCOVA) model will be estimated on the changes from baseline to Week 8 considering planned treatment group as factor and baseline value of the parameter as continuous covariate. Results will be reported as Least-Square Means together with associated two-tailed 95% CI; the difference between Least

Square Mean of nutraceutical combination group versus placebo will be estimated with two-tailed 95% CI and p-value.

If the assumption of normality of residuals is violated, the ANCOVA model will be fitted on rank transformed data.

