6.5.4. Exploratory efficacy analysis

The following exploratory efficacy analysis will be performed on the FAS population:

- Summary statistics of LDL cholesterol levels and change from baseline at each assessment time point will be presented focusing on patient subgroups of clinical interest.
 - Patients with baseline levels of LDL cholesterol
 - Ranging from 115 mg/dl to 159 mg/dl
 - Equal or greater than 160 mg/dl
 - Patients with baseline values of eGFR (computed according to the MDRD formula)
 - Ranging from 60 and 89 ml/min/1.732m²
 - Equal or greater than 90 ml/min/1.732m²
 - Patients with/without Metabolic Syndrome
According to the 2009 Joint Interim Statement, the Metabolic Syndrome is defined as the presence of an abdominal circumference >102 cm for men or >88 cm for women, and two or more of the following criteria:
 - Glucose in fasting conditions ≥ 100 mg;
 - SBP ≥ 135 mmHg or DBP ≥ 85 mmHg or current treatment with antihypertensive drugs;
 - Triglycerides >150 mg/dl;
 - HDL <40 mg/dl for men, <50 mg/dl for women
 - Patients with/without glucose in fasting conditions altered, defined as glucose in fasting conditions out of the following range: from 100 mg/dl and 125 mg/dl.
 - Patients with/without proved hypertension, i.e. patients with SBP ≥ 140 mmHg and/or DBP ≥ 90 mmHg for three consecutive readings performed in orthostatic position.
- Linear regression analysis on LDL change at Week 8 vs. baseline will be performed considering patients age, gender and BMI as predictors.
In case of violation of the assumption of normality of residuals, the linear regression model will be fitted on appropriate transformed data (i.e. rank transformed data, logarithmic transformed data).
- Linear regression analysis on LDL change at Week 8 vs. baseline will be performed considering patients eGFR and glycemia values at baseline as predictors.

Statistical Analysis Plan

Sponsor: A. Menarini Industrie Farmaceutiche Riunite S.r.l.

Protocol number: MEIF/16/MOF-Col/001

In case of violation of the assumption of normality of residuals, the linear regression model will be fitted on appropriate transformed data (i.e. rank transformed data, logarithmic transformed data).

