- Linear regression analysis on endothelial reactivity change at Week 8 vs. baseline will be performed considering patients age, gender and BMI as predictors. In case of violation of the assumption of normality of residuals, the linear regression model will be fitted on appropriate transformed data (i.e. rank transformed data, logarithmic transformed data).
- Linear regression analysis on endothelial reactivity change at Week 8 vs. baseline will be performed considering patients eGFR and glicemia values at baseline as predictors.

In case of violation of the assumption of normality of residuals, the linear regression model will be fitted on appropriate transformed data (i.e. rank transformed data, logarithmic transformed data).

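### Minor: the four exploratory regressions in SAP 6.5.4 pool both arms without a treatment term, which costs precision that one added term would recover

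*SAP*

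**What the plan says.** SAP 6.5.4 opens with the population: "The following exploratory efficacy analysis will be performed on the FAS population". It then lists four linear regressions.

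1. "Linear regression analysis on LDL change at Week 8 vs. baseline will be performed considering patients age, gender and BMI as predictors".
2. "Linear regression analysis on LDL change at Week 8 vs. baseline will be performed considering patients eGFR and glycemia values at baseline as predictors".
3. "Linear regression analysis on endothelial reactivity change at Week 8 vs. baseline will be performed considering patients age, gender and BMI as predictors".
4. Endothelial reactivity change again, "considering patients eGFR and glicemia values at baseline as predictors".

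None of the four names treatment group or the baseline value of its outcome. Nothing elsewhere in the SAP or protocol adds these terms or says that the regressions are run separately by arm.

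The confirmatory-style models for the same outcomes are built differently. The LDL model in SAP 6.5.1 is fitted "considering planned treatment group as factor and baseline value of LDL cholesterol as continuous covariate". The models in SAP 6.5.3, which cover the pulse volume measure of endothelial reactivity, are fitted "considering planned treatment group as factor and baseline value of the parameter as continuous covariate".

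**The concern.** The full analysis set contains both arms. The trial is sized on the expectation that the arms differ by 15 mg/dL in LDL change. A regression that ignores arm treats that expected difference as unexplained scatter, so the standard error of every coefficient is larger than it need be. With about 70 evaluable patients there is little precision to give away, and the variable that would recover it is known for every randomized patient.

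The missing baseline term raises a separate question. Change from baseline carries regression to the mean, so a predictor related to baseline LDL may appear related to change for that reason alone. Whether adding baseline cures this or causes the opposite problem depends on facts that the documents do not give.

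**Working it through.** **Inputs.** From SAP 3.6: "Assuming a baseline LDL level of 145 ± 19 mg/dL", an arm difference of 15 mg/dL, 90% power, two-sided 5% alpha, 35 evaluable per arm, 20% dropout. From SAP 3.3: eligibility LDL of 115 to 190 mg/dL, confirmed on the Visit 2 sample, which is also the baseline value. Assumed, because the documents do not give it: the correlation ρ between Visit 2 and Visit 4 LDL, taken as 0.5, 0.7 and 0.9.

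**The plan's own figure.** Using 19 mg/dL as the SD of change, a two-sample comparison of 15 mg/dL needs 34 per arm by the normal approximation and 35 by the t-test (power 0.902). Then 35/0.8 = 43.75, rounded up to 44 per arm, 88 in total. The stated figure reproduces. If 19 mg/dL is both the baseline SD and the SD of change, then 19² = 2 × 19² × (1 − ρ), so ρ = 0.5.

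**Cost of leaving out arm.** With 1:1 allocation, an arm difference δ left in the residual adds δ²/4 to its variance: 15²/4 = 56.25.

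A normal baseline of 145 ± 19 truncated to 115–190 has SD 16.29 (variance 265.5). The residual variance of change with arm in the model, but not baseline, is 19²(1 − ρ²) + (1 − ρ)² × 265.5.

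| ρ | With arm term | As written (+56.25) | Ratio | Equivalent n = 70/ratio |
|---|---|---|---|---|
| 0.5 | 270.8 + 66.4 = 337.1 | 393.4 | 1.17 | 60 |
| 0.7 | 184.1 + 23.9 = 208.0 | 264.3 | 1.27 | 55 |
| 0.9 | 68.6 + 2.7 = 71.2 | 127.5 | 1.79 | 39 |

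Without truncation at ρ = 0.5, the variance is 361 with arm and 417.25 without, a ratio of 1.16 and an equivalent n of about 61. The size of the arm difference matters more. At ρ = 0.5 with truncation, 10 mg/dL gives 70 × 337.1/(337.1 + 25) = 65 patients, and 20 mg/dL gives 70 × 337.1/(337.1 + 100) = 54. With no arm difference nothing is lost.

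Because allocation is random, arm is unrelated to the predictors on average. The omission therefore widens intervals but does not bias coefficients. In simulation a predictor unrelated to baseline was rejected at about the nominal 5% with or without the arm term.

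**Baseline: two data models, opposite answers.** Let r be the predictor's correlation with the measured Visit 2 value, s = 19, and suppose that the predictor has no effect of its own on change. Ignoring truncation:

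- *Predictor tracks the measured Visit 2 value.* Without baseline, the slope per SD of predictor is −(1 − ρ)rs. At ρ = 0.5 and r = 0.3 this is −0.5 × 0.3 × 19 = −2.85 mg/dL. With baseline it is 0.
- *Predictor tracks the patient's stable level*, with Visit 2 and Visit 4 each equal to that level plus independent noise. Without baseline, the slope is 0. With baseline it is +(1 − ρ)rs/(1 − r²) = 2.85/0.91 = +3.13 mg/dL.

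Simulated rejection rates at nominal 5% (35 per arm, 15 mg/dL effect, Visit 2 truncated to 115–190, predictor correlated 0.3 with the measured value or with the stable level respectively), at ρ = 0.5/0.7/0.9:

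| Predictor tracks | As written | Arm and baseline added |
|---|---|---|
| Measured Visit 2 value | 14/10/6% | about 5% |
| Stable level | about 5–6% | 18/14/8% |

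Adding arm alone leaves the first row's as-written rates no lower and the second row's at about 5–6%. It neither cures nor causes the baseline problem.

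**Endothelial reactivity.** The documents give no SD, expected effect or correlation, so no figure can be put on regressions 3 and 4. The reasoning about the arm term is the same if the product changes reactivity.

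**The case against.** The strongest reply is that these are exploratory models in a study labelled exploratory, that no decision in the documents rests on them, and that SAP 2.3 frames the aim as comparing LDL decrease between groups defined by baseline characteristics. That stands, and it is why the point is minor. It is not a reason to keep a model that discards precision at no benefit.

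A second reply is that an analyst might fit the models by arm anyway. Nothing in 6.5.4 says so, and the section names only the full analysis set.

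A reader might infer more than the documents support, in three ways.

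- *That both arm and baseline must be added, because the models as written yield false positives.* That holds only if predictors track the measured Visit 2 value. If age, gender or BMI track the stable LDL level, adding baseline produces the false positives. The documents cannot say which applies.
- *That the precision loss should be counted against a model with both terms.* That residual-variance comparison overstates the gain for a predictor correlated with baseline, because sharing information with baseline gives part of the gain back. In a three-predictor simulation at ρ = 0.5, adding both terms cut the standard error for age from 2.43 to 2.06. For BMI, correlated 0.3 with baseline, it went only from 2.43 to 2.16.
- *That the regressions were meant to identify responders.* Nothing in 6.5.4 claims this, and neither a treatment nor a baseline main effect would deliver it.

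**Conclusion.** The point holds as a minor improvement. The four regressions omit planned treatment group, and the SAP's own models for the same outcomes include it. For LDL, the omission inflates residual variance by 17%, 27% or 79%, so that 70 patients do the work of about 60, 55 or 39, at an assumed ρ of 0.5, 0.7 or 0.9. These figures assume that the 15 mg/dL difference occurs and that baseline LDL is 145 ± 19 truncated to the eligibility range. The smallest loss belongs to ρ = 0.5, the value implied if 19 mg/dL serves as both the baseline SD and the SD of change. The largest rests on a correlation that is purely assumed. The loss for endothelial reactivity is unquantified.

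The case for the arm term does not depend on which baseline model is true. The case for the baseline term does, so neither version alone should be read as showing an effect on change. In either version the coefficients are prognostic associations, not differential response to the product.

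**What to change.** In SAP 6.5.4:

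- Add planned treatment group as a factor to all four regressions.
- Report each model twice, with and without the baseline value of its outcome (baseline LDL, or baseline pulse volume measure). State that an association seen in only one version may be an artefact of how the predictor relates to baseline.
- State that the coefficients describe prognostic association across both arms.

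The cost is a few lines of SAP wording, one degree of freedom per model for arm, one more in the versions with baseline, and four extra model outputs. All variables are already collected.

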6.6. SAFETY EVALUATION

Safety analyses will be conducted on the Tolerability Population.

6.6.1. Adverse Events

According to the onset date of the event, AEs will be defined as follows:

- treatment-emergent AE, those events with an onset date after treatment initiation
- non-treatment-emergent AE, those events with an onset date between informed consent and treatment initiation

The incidence of Adverse Events (AEs) and Serious Adverse Events (SAEs) recorded throughout the study will be presented by actual treatment. Non treatment-emergent AEs will be listed separately.

Tables reporting a general summary of AEs will be produced specifying the number of total events and the absolute and relative frequency of subjects with AEs. As a patient may have more than one AE, the total number of AEs could be greater than the total number of patients. Absolute and relative frequency of patients with drug-related AEs, severe AEs, SAEs, AEs with an outcome of death, AEs leading to temporary or permanent discontinuation of treatment will be also reported. Product-related AEs will be the AEs with causality equal to “certain”, “probable”, “possible” or “unassessable”; if the relationship to study treatment is missing, the treatment-emergent AE will be considered drug related as well. AEs leading to temporary or permanent discontinuation of treatment will be the AEs with action taken with investigational product equal to “Drug interrupted” or “Drug withdrawn.”

Statistical Analysis Plan

Sponsor: A. Menarini Industrie Farmaceutiche Riunite S.r.l.

Protocol number: MEIF/16/MOF-Col/001

Treatment-emergent AEs will be summarized by MedDRA dictionary System Organ Class (SOC) and Preferred Term. A summary of treatment-emergent AEs by preferred term and severity will be also provided.

All related treatment-emergent AEs, treatment-emergent AEs with an outcome of death, treatment-emergent AEs leading to discontinuation of treatment will be summarized by MedDRA dictionary System Organ Class (SOC) and Preferred Term (PT) and will also be listed.

Serious treatment-emergent AEs will be summarized similarly.

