**2.2 Study Flow Chart**

	Day -14	Day 0	Day 28 (± 3)	Day 56 (± 3)
	Visit 1 ^	Visit 2 ^§	Visit 3 ^	Visit 4 ^
	Screening	Baseline	Intermediate	End of study
Informed consent	✓			
Inclusion/exclusion criteria	✓	✓		
Medical history	✓			
Weight, height & , waist circumference, Index of Central Obesity (ICO), Body Mass Index (BMI), Hepatic Steatosis Index (HSI), Lipid Accumulation Product (LAP)	✓	✓	✓	✓
Heart rate, blood pressure #	✓	✓	✓	✓
Hematology/clinical chemistry *	✓	✓	✓	✓
Urine Pregnancy Test (dipstick)		✓		✓
Endothelial reactivity (Endocheck)		✓		✓
Diet evaluation +	✓	✓	✓	✓
Randomization/Dispensation of treatment		✓ °		
Compliance with treatment			✓	✓
Concomitant medications	✓	✓	✓	✓
Adverse events (AE)		✓ †	✓	✓

^ Visits to take place in the morning. Participants will be asked to fast overnight 12h before the visits.

# Orthostatic and clinostatic, diastolic and systolic blood pressure (average of three measurements).

\* Full lipid panel (total cholesterol, LDL-cholesterol, HDL and non-HDL cholesterol, triglycerides, risk ratio, B apolipoproteins, LDL-C/Apo B), glycemia, ALT, AST, gamma-GT, CPK, uric acid, creatinine, eGFR with MDRD formula.

§ During Visit 2 – Baseline evaluation – the LDL-C and TG values will be confirmed through a blood test analysis. If the eligibility was confirmed, the patient will be asked to return no later than 3 days after V2 for randomization and treatment dispensation.

† Collection of AEs occurred after signature of informed consent.

& Height only at Visit 1.

+ See Appendix 1 of the protocol for diet guidelines.

° Randomization and dispensation of treatment will take place within 3 days from Visit 2^ - Baseline evaluation and will be considered as “Day 0”.

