## 10. ASSESSMENT OF SAFETY

### 10.1 Adverse events (AE)

An adverse event (AE) is any untoward medical occurrence in a patient administered the product and which does not necessarily have to have a causal relationship with the product.

Adverse events should be recorded in the Adverse Events CRF under the signs, symptoms or diagnosis associated with them accompanied by the following information.

- severity grade
  - mild: usually transient in nature and generally not interfering with normal activities
  - moderate: sufficiently discomforting to interfere with normal activities
  - severe: prevents normal activities
- Relationship to the investigational product (no/yes)
- Duration (start and end dates) or if the event is ongoing an outcome of not recovered/not resolved should be reported.
- Action taken regarding investigational treatment
- Whether other medication or therapies have been taken
- Outcome (not recovered/not resolved; recovered/resolved; recovering/resolving, recovered/resolved with sequelae; fatal; or unknown)
- Whether it constitutes a serious adverse event (SAE)

A **serious adverse event** (SAE) is any untoward medical occurrence that at any dose:

- Results in death, or
- Is life-threatening, or
- Requires inpatient hospitalization or prolongation of existing hospitalization, or
- Results in persistent or significant disability/incapacity, or

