### **Adverse Events**

The incidence of Adverse Events (AEs) and Serious Adverse Events (SAEs) recorded throughout the study will be presented.

According to the onset date of the event, AEs will be defined as follows:

- treatment-emergent AE, those events with an onset date after treatment initiation
- non-treatment-emergent AE, those events with an onset date between informed consent and treatment initiation

Non treatment-emergent AEs will be listed only.

Treatment-emergent AEs will be summarized by MedDRA dictionary system organ class and preferred term. A summary of treatment-emergent AEs by preferred term and severity will be also provided. For analysis purposes, all treatment-emergent AEs defined as “certain”, “probable”, “possible” or “unassessable” will be considered as product related. If the relationship to study treatment is missing, the treatment-emergent AE will be considered treatment-related. All related treatment-emergent AEs, treatment-emergent AEs with an outcome of death, treatment-emergent AEs leading to discontinuation of treatment will be summarized by MedDRA dictionary system organ class and preferred term and will also be listed. Serious treatment-emergent AEs will be summarized similarly. Percentages will be based on the number of subjects in the Tolerability set.

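### Treatment-emergent AEs are defined by onset date alone, so a screening-period event that worsens on treatment can be missing from the treatment-emergent tables

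*SAP*

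**What the plan says.** SAP 6.6.1 opens its classification with "According to the onset date of the event, AEs will be defined as follows". The two classes are "treatment-emergent AE, those events with an onset date after treatment initiation" and "non-treatment-emergent AE, those events with an onset date between informed consent and treatment initiation". Protocol 11.5, under Adverse Events, uses the same two classes. Neither text mentions an event that begins before treatment and then worsens.

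The classes are reported differently. The protocol states that "Non treatment-emergent AEs will be listed only"; the SAP states that "Non treatment-emergent AEs will be listed separately". The detailed tables are tables of treatment-emergent events. For example, the SAP says "A summary of treatment-emergent AEs by preferred term and severity will be also provided", and both documents add tables by system organ class and preferred term, and of related, fatal, discontinuation-leading and serious treatment-emergent events.

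SAP 6.6.1 also describes a general AE summary by actual treatment. It covers total events and patients with related, severe, serious, fatal and discontinuation-leading AEs, and its wording does not limit it to treatment-emergent events.

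On recording, the flow chart in Protocol 2.2 notes "Collection of AEs occurred after signature of informed consent". Protocol 10.1 asks for a severity grade for each event, and for "Duration (start and end dates) or if the event is ongoing an outcome of not recovered/not resolved should be reported". It does not say how an increase in severity is to be recorded.

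**The concern.** Worsening of a complaint after the product is started is one of the things a tolerability comparison should show. Under an onset-only rule, the class of an event is fixed before the patient takes a tablet, and nothing that happens later can change it. A patient with a mild muscle ache in screening that becomes severe on treatment has a non-treatment-emergent event throughout.

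The case is plausible in this trial. The protocol describes monacolins as HMG-CoA reductase inhibitors, excludes patients with myopathies, and measures CPK and transaminases at every visit. If the product did cause worsening, more events would be omitted from the active arm than from placebo, and the treatment-emergent tables would make the product look better tolerated than it was.

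**Working it through.** The plan states no figure on this point, so the check is of the texts side by side, with a little arithmetic for scale.

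**1. Can pre-treatment events exist in the database?** Yes. Collection starts at consent (Protocol 2.2). Visit 1 is at Day -14, and randomization with dispensation takes place 0 to 3 days after Visit 2.

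- Shortest window: 14 + 0 = 14 days. Share of the time from consent to Day 56: 14 / (14 + 56) = 14/70 = 20%.
- Longest window: 14 + 3 = 17 days. Share: 17 / (17 + 56) = 17/73 = 23%.

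**2. Is a worsening dated as a new event?** Nothing in either document says so. Protocol 10.1 takes start and end dates per event and has the investigator follow each AE until recovery or stabilisation, which fits one continuing record with one onset date. The protocol does not forbid a new record either.

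**3. Trace one case.** Take a hypothetical symptom AE with mild onset at Day -7 that becomes severe at Day 20 and is kept under one record. Its onset precedes treatment initiation, so it is non-treatment-emergent.

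| Output | Event included? |
|---|---|
| Treatment-emergent AEs by system organ class and preferred term | No |
| Treatment-emergent AEs by preferred term and severity | No |
| Related, fatal, discontinuation-leading and serious treatment-emergent AEs | No, even if it meets the criterion |
| Listing of non-treatment-emergent AEs | Yes |
| General AE summary (SAP 6.6.1) | Possibly, if the summary covers all AEs and the record is updated |

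The last row exposes an inconsistency. An event of this kind that led to withdrawal of the product could be counted in the general summary and yet be missing from the table of discontinuation-leading events by preferred term, so the two would not agree.

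**4. Is the information available elsewhere?** For laboratory values, largely yes. CPK, ALT and AST are secondary variables with an ANCOVA on change from baseline to Week 8 (SAP 6.5.3). They are also summarised as change from baseline at each time point and as low, normal or high (SAP 6.6.2). Symptoms such as muscle ache have no such second route.

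**5. Scale.** The documents give no rate of screening-period AEs or of worsening, so the number affected cannot be computed. As a pure assumption, suppose 10% to 20% of 90 patients have an AE in the window and 10% to 20% of those worsen on treatment:

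- 90 × 0.10 × 0.10 = 0.9 events
- 90 × 0.20 × 0.20 = 3.6 events

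That is for both arms together and for any cause; halved, about 0.5 to 1.8 per arm. With 45 patients per group (Protocol 6), one patient is 1/45 = 2.2 percentage points in an incidence table.

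**The case against.** Four counter-arguments deserve weight.

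**The event is not lost altogether.** A reader might infer that it disappears from every count. The documents do not support that. It stays in the listing, and the general summary, read plainly, can count it by arm under related, severe, serious or discontinuation. This stands. It limits the point to the treatment-emergent tables, and mainly to detail at preferred-term level.

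**CPK and ALT are compared between arms anyway.** A reader might infer that a muscle or liver signal would go unseen. For laboratory values that is wrong, as step 4 of the working shows. The one qualification is that the low/normal/high counts do not move when a value already high rises further; the change-from-baseline analyses still reflect it. The point therefore rests on symptoms.

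**A new AE line may already be required.** Protocol 13.2 refers to CRF user guidelines, which are not among the documents. If they call for a new line at worsening, its onset date makes the event treatment-emergent under the present rule. This is possible, and the point is therefore conditional on one continuing record. It does not remove the point, because neither document states the convention on which the definition depends.

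**Few events are involved.** Complaints already ongoing at consent go to medical history (SAP 6.2). What remains must start within about two weeks and then worsen within eight. This stands. A reader might also infer that the omitted events are a material share of related AEs. That cannot be shown: the rates are assumed, and the illustrative count covers all causes in both arms, so it cannot be set against related events in one arm.

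**Conclusion.** The point holds as a gap in definition. Applied as written, the onset-only rule keeps an AE that begins between consent and first intake, and later increases in severity or becomes serious, out of every treatment-emergent table. This rests on one assumption: that the worsening is kept under the existing record, on which both documents are silent.

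The consequence is modest. The number of events is unknown and probably small, the AE reporting is descriptive, and no efficacy result is affected. Any bias between arms is conditional on the product causing worsening, which the documents neither show nor exclude. It is a cheap improvement to the tolerability analysis, not a flaw that undermines it.

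**What to change.** 1. In SAP 6.6.1 and Protocol 11.5, extend the treatment-emergent definition with: *or an event with onset before treatment initiation that increases in severity grade or becomes serious after treatment initiation*.
2. Choose one recording convention for worsening and state it: either the existing record is updated with the date of worsening, or a new AE line is opened. Using both without a rule could count one episode twice, once through the widened definition and once through the new line. State that each episode is counted once.
3. State in SAP 6.6.1 whether the general AE summary covers all recorded AEs or only treatment-emergent ones, so that its totals can be reconciled with the detailed tables.

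Cost: a short SAP edit, a CRF instruction, and a minor protocol amendment, which under Protocol 14.1 goes to the Ethics Committee for approval before implementation. Treatment-emergent counts may rise slightly. Visits, sample size and efficacy analyses are unchanged.
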